7.1 Adverse event definition

Since the patients signed informed consent to the completion of all visits, the patients to report or research physician observed any adverse medical events, regardless of whether there is a causal relationship with the test drugs, were convicted of adverse events. Adverse events included general adverse events, adverse events and serious adverse events.

7.2 Ways of getting information about adverse events

All the adverse events report in directly medical terminology report.

7.3 Record of adverse events

Record the occurrence of adverse events, severity, duration, and outcome measures. Adverse events should be recorded in the specified CRF adverse event reporting table.

When the adverse events appear, the researcher should immediately report to the responsible party and determine the necessary diagnosis and treatment according to the condition of the patient to decide whether to stop the clinical trial. All adverse events should be followed up, and the treatment process and results should be carefully recorded until the proper solution or the condition is stable, and the correlation between the method and the test method is determined. If associated with surgery, should be tracked to return to preoperative levels. Follow up visits can be done according to the severity of adverse events such as hospitalization, outpatient visits, home visits, telephone calls, communication, etc..

7.4 Criteria for severity of adverse events

When completing the CRF adverse event table, the researchers referred to the CTCAE4.0 criteria to describe the intensity of adverse events using mild, moderate, severe, life-threatening, and fatal events. For a unified standard, classification of event intensity of light moderate and severe criteria are as follows:

Mild: does not affect the normal function of patients;

Moderate: to a certain extent affect the normal function of patients;

Severe: normal function of affected patients.

Pay attention to the difference of adverse events and severity of strength. Used to describe the severe intensity, not necessarily SAE. For example, headache may be severe in intensity, but not in SAE unless it meets SAE criteria.

7.5 The judgment standard of adverse events and test operation relations

Evaluation according to the following interpretation.

It was confirmed that the adverse events were accorded with the reasonable time after the trial operation, and the reaction accorded with the type of reaction known in the test operation;

It is likely that the adverse events are accorded with the reasonable time after the trial operation, that the response conforms to the type of reaction known to the test operation, and that there is unlikely to be additional explanation, such as concomitant medication or concomitant disease;

It may be related to the occurrence of adverse events that are consistent with the time order of the trial operation, the response to the type of reaction known to the test operation, and the patient's clinical status or other treatment modalities may also reaction of operation;

It may be irrelevant: adverse events do not conform to the reasonable time sequence after the trial operation, and the reaction is not in line with the known type of reaction in the test operation; it is more likely to be related to other factors;

Certainly nothing: the reaction does not comply with the time sequence test operation after reasonable, a type of reaction with non test operation known reaction; the patient's clinical status or other treatment may cause the reaction, improve the disease state or stop the elimination reaction of other treatments, the repeated use of other treatment response.

Certainly, adverse reactions may be associated and may be related to all adverse events.

7.6 Important adverse events

Serious adverse events (SAE) that required hospitalization, prolonged hospitalization, disability, affecting work ability, endanger life or death, resulting in congenital malformation occurred during the clinical trial.

7.7 Plans to deal with cases of serious adverse events

When serious adverse events occur, we should do our best to save them and take all kinds of measures to avoid permanent damage. From the beginning of project to any SAE appear in the observation period, the researchers shall immediately notify the person in charge of project in our hospital, clinical trial management, ethics committee, fill out the "serious adverse events", 24h in a written report to the applicant, our hospital clinical trial management

Project name:Arthroscopic Assisted Balloon Tibioplasty for the Treatment of Schatzker II-IV Tibial Plateau Fractures

Version number 1.1

departments, the ethics Committee and relevant drug management department. Serious adverse events in the end of treatment, the patients should be submitted to the follow-up report

Contacts for serious adverse events

unit	linkman	contact way
Project Leader	[name]	[name] [contact]
The Second Affiliated Hospital of Wenzhou Medical University	Medical ethics committee	[name] [contact]
The Second Affiliated Hospital of Wenzhou Medical University	The clinical research center for drug clinical trial institution Office	[name] [contact]

8. Statistical analysis

8.1 Data selection for statistical analysis

Totally analyzed data sets (FAS): all randomized, grouped, and postoperative studies were performed with a complete analysis set. For the therapeutic data that failed to be observed in all treatments, the final measured efficacy data was used as end point data for analysis.

PPS (PPS): contained in the FAS, met the inclusion criteria, does not meet the exclusion criteria, no major protocol violations, and has completed the treatment period of efficacy evaluation, good compliance cases, this study constitutes with the scheme set.

Safety analysis data set (SS): all patients who were randomized to receive research methods and had postoperative safety evaluation data constituted the safety analysis data set of this study.

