[figure not shown]
Research topics	Arthroscopic Assisted Balloon Tibioplasty for the Treatment of Schatzker II-IV Tibial Plateau Fractures
purpose	Objective to compare the clinical diagnosis and treatment of open reduction and internal fixation with Schatzker II-IV tibial plateau fracture or arthroscopic assisted balloon tibioplasty of tibial plateau fractures.
overall design	This study used a randomized controlled trial design research.
diagnostic criteria	At least 2 fixed researchers by X-ray or CT examination to determine fracture type
Screening criteria	
Inclusion criteria: The following criteria must be according with.
 
(1) fresh closed fracture, X-ray and CT examination diagnosed Schatzker type II-IV tibial plateau fracture patients(2) sign the informed consent form(3) age from 18 to 80 years 
Exclusion criteria:
 
(1) exclude open fractures, pathological fractures, immunodeficiency, hematological diseases and severe hepatorenal disorders(2) refuse to sign informed consent form

Methods	
Experimental group: patients were randomly divided into the experimental group and underwent Arthroscopic Assisted Balloon Tibioplasty.
 
Control group: patients were randomly divided into control group and underwent Open Reduction and Internal Fixation(ORIF).

Curative effect observation index	
Primary Outcome Measure:
 
1.Rasmussen scores change after surgery the knee joint Rasmussen scores change after surgery [Time Frame: 1、2、3、4、6、12mouth Rasmussen scores change after surgery]
 
Secondary Outcome Measures:
 
1.Intraoperative blood loss blood loss in surgery [Time Frame: Operation day]
 
2.Postoperative pain score Postoperative pain score(Visual Analogue score, range of scores from 0 to 10, the score is designed to measure the level of the pain and the higher score is, the more painful the patient is) [Time Frame: from operation day to leave hospital day(up to 2 weeks)]
 
3.Fracture healing time Fracture healing time [Time Frame: from leave hospital day to healing time(up to 1 year)]
 
4.The percentage of joint area recovered after operation was

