	
satisfactory
 
The percentage of joint area recovered after operation was satisfactory
 
[Time Frame: 1、2、3、4、6、12 mouth after surgery]
 
5.operation time
 
Duration of surgery
 
[Time Frame: Operation day]
 
6.the postoperative hospital stay days
 
the total hospital stay days after surgery
 
[Time Frame: from operation day to Leave hospital day(up to 4 weeks)]

Safety observation index	Intraoperative vital signs, Intraoperative C arm examination, postoperative examination etc.
Visiting point	Screening / baseline: admission to the preoperative / postoperative day from the first day to the day of discharge. 1、2、3、4、6、12 mouths after the operation.
statistical analysis	Spss22.0 software was used for statistical analysis. The measurement data in SX, using t test, count data expressed as a percentage, using X - test, $P < 0.05$, the difference has statistical significance, and draw the relevant charts with RevMan software. Case characteristics and efficacy analysis were analyzed by complete analysis set (FAS) and compliance program set (PPS), and safety evaluation was analyzed by safety set (SS).
sample size	A total of 40 patients were included this project, the experimental group 20 cases and the control group 20 cases.
Research cycle	July 2017 ~ June 2020

Technology Roadmap

Technology Roadmap

Project text

1. Research topics

Arthroscopic Assisted Balloon Tibioplasty for the Treatment of Schatzker II-IV Tibial Plateau Fractures

2. Research background

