4.3 Exit criteria

The patients were lost, half-way to quit and other unpredictable problems

5. Project design

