5.2 Screening period (from admission to day before surgery)

- 1) come to our hospital after injury, meet the inclusion criteria.
- 2) at least 2 permanent investigators confirm the type of fracture by X-ray or CT examination.
- 3) after signed the informed consent form, according to random table method, the patients were randomly divided into experimental group or control group for corresponding treatment.

5.3 During the study period (from the day of surgery to 1 years after surgery)

- 1) the day of surgery recorded in detail the surgical procedures, operation time, intraoperative blood loss were recorded.
- 2) from operation day to leave hospital day(up to 2 weeks),the postoperative pain score, postoperative knee gap width, postoperative hospital stay days were recorded.
- 3) the patients were followed up after leave hospital: make a detailed record of the knee joint Rasmussen scores change after surgery (Rasmussen score) (1,2,3,4,6,12 months after surgery), The

percentage of joint area recovered after operation where was satisfactory, postoperative fracture healing time, maximal postoperative articular surface collapse height, postoperative failure rate and related complications.

5.4 The end of the study period (the end of the follow-up to the project end)

1. sort the appropriate information, through epidemiological or statistical experts guidance, experimental group and control group data analysis, using SPSS 22.0 statistical software analysis, measurement data to sx, using t test, counting data Percentage, using χ^2 test, $P <0.05$ for the difference was statistically significant, and use RevMan software to draw the relevant charts.
2. based on the data and charts after treatment, organize clinical discussions and experience of relevant personnel: 1.the actual operation of the new technology found in all aspects of the existing shortcomings and explore ways to improve the arthroscopic balloon dilatation tibial angioplasty, and improve the clinical diagnosis and treatment of fractures related to our hospital level. 2 through get the follow-up data under this new technology to enrich our hospital clinical data resources.

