6.1 The main efficacy indicators

Operation time (min)

Postoperative hospital stay (d) (first day after surgery to discharge day, up to 4 weeks)

Postoperative knee function Rasmussen score changes (1, 2, 3, 4, 6, 12 months)

6.2 secondary efficacy indicators

Intraoperative bleeding (ml)

Postoperative pain score (visual analogue scale (VAS)) (first postoperative day to discharge day, maximum 2 weeks)

Postoperative fracture healing time (m) (discharged to fracture healing, maximum 1 year)

Postoperative knee gap width (mm)

Postoperative articular surface maximum collapse height (mm)

Height of well-resumed postoperative articular area as a percentage of collapse area (%)

7. Safety evaluation

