8.2 Statistical analysis plan

There was no significant difference in age, gender, fracture type and other aspects between the two groups ($P>0.05$). Through epidemiological or statistical expert guidance, the experimental group and the control group data were analyzed using SPSS 22 statistical software, the measurement data in SX, using t test, count data expressed as a percentage, using X - test, $P < 0.05$, the difference has statistical significance, and draw the relevant charts with RevMan software.

9. Data management and statistical analysis

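### Carrying the last value forward is the full analysis set's only missing-data rule; it biases the knee-score comparison whenever share lost times recovery still to come differs between arms

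*Combined protocol and SAP*

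**What the plan says.** Section 8.1 defines the full analysis set (FAS) and adds that, where efficacy was not observed throughout, "the final measured efficacy data was used as end point data for analysis". The rule does not vary with the reason for loss, its timing or the arm.

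The outcome most exposed is the knee score. Section 6.1 lists "Postoperative knee function Rasmussen score changes (1, 2, 3, 4, 6, 12 months" among three main indicators, and section 5.3 schedules the same visits. The project abstract makes the Rasmussen score its only primary outcome. The other two main indicators, operation time and postoperative stay, are known by discharge and are barely touched by the rule.

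The analysis is a t test (section 8.2: "the measurement data in SX, using t test"). The abstract adds "Case characteristics and efficacy analysis were analyzed by complete analysis set (FAS) and compliance program set (PPS", and section 8.1 restricts the per-protocol set (PPS) to patients without major violations who "has completed the treatment period of efficacy evaluation, good compliance cases". Section 4.3 foresees exits ("The patients were lost, half-way to quit and other unpredictable problems") but gives no rate and no analysis rule. Section 9.1 on completing the case report form concerns data entry, not missing visits. No mixed model, multiple imputation or sensitivity analysis appears.

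**The concern.** After fracture surgery a knee score is expected to rise over the year. LOCF records a patient last seen at month 3 as having the month 3 level at the end. Each arm's mean is pulled down by its share lost times the recovery those patients had still to make. If that product differs between arms, whether through the amount of loss, its timing or the remaining recovery, the comparison reports a difference in attendance or in pace of recovery as a difference in final knee function.

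There is a second cost. Mixing early and final values within an arm widens the spread, so power falls even when the arms lose patients equally. With 20 patients per arm there is little to spare.

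**Working it through.** **The plan's own figure.** Section 3.3 gives 40 patients, 20 per arm, with no effect size, SD, power or dropout allowance, so there is nothing to reproduce.

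**Bias formula.** For loss unrelated to outcome, with p the share lost and g the mean recovery still to come at the last visit seen, the bias in experimental minus control is pC × gC − pE × gE. It is zero when the products match or g = 0.

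**Assumed inputs (none is in the documents).** Analysis at month 12; means 14, 17, 20, 22, 25, 27 at months 1, 2, 3, 4, 6, 12 in both arms (the steep course); SD 3; correlation 0.6; two-sided 5% t test; each patient lost at random with the stated probability. Recovery still to come after month 3 / 4 / 6 is 27 − 20 = 7, 27 − 22 = 5 and 27 − 25 = 2 points.

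**Bias and simulated type I error, no true difference at month 12:**

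| Loss, experimental v control | Last seen | Bias (points) | Type I error |
|---|---|---|---|
| 10% v 15% | month 3 / 4 / 6 | 0.05 × 7, 5, 2 = 0.35 / 0.25 / 0.10 | 5.8 / 5.5 / 5.2% |
| 5% v 20% | month 3 / 4 / 6 | 0.15 × 7, 5, 2 = 1.05 / 0.75 / 0.30 | about 13 / 10 / 6% |
| 15% v 15% | month 6 v month 3 | 0.15 × 7 − 0.15 × 2 = 0.75 | about 9% |

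Swapping the arms reverses the sign. In the third row the amount of loss and the curves are identical; timing alone creates the bias.

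**Random probability is not a fixed count.** If exactly 1 v 4 patients are lost, the bias is the same but the type I error is about 8 / 7 / 5%. With exactly 2 v 3 lost it is about 2.0 / 3.0 / 4.6%, below nominal. With fixed counts, the spread between carried and observed values inflates the estimated variance without adding to the sampling variance of the difference.

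**Other assumed inputs, 5% v 20% loss.** A flatter course (18, 21, 23, 24.5, 26, 27) gives 0.60 / 0.37 / 0.15 points and about 9 / 7 / 5%. The steep course with SD 5 gives about 9 / 7 / 5%.

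**Power, equal 15% loss at the same visit.** Take a constant true difference of 2.73 points, which gives 80% with complete data. The variance under LOCF becomes 9 + 0.15 × 0.85 × g²:
- month 3: 9 + 0.1275 × 49 = 15.25, SD 3.90, power 58%
- month 4: 9 + 0.1275 × 25 = 12.19, SD 3.49, power about 68%
- month 6: 9 + 0.1275 × 4 = 9.51, SD 3.08, power 78%

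Completers alone have about 73%. A mixed model has 78% with compound symmetry and 76–77% with an unstructured covariance. On the flatter course LOCF has 72 / 76 / 80%.

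**Is the PPS a check?** Suppose 15% per arm are lost, with loss tied to the last observed score: low scorers lost in control, high scorers in the experimental arm. Completers are then biased by about −0.51 points and LOCF by about +0.29, while the mixed model stays within 0.01. Two biased analyses lie on either side of the truth, and comparing them does not settle the answer.

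**The case against.** **The size is speculative.** This stands. Curve, SD, correlation, dropout, imbalance and analysis visit are all assumed. At 10% v 15% loss the bias is at most 0.35 points, against 2.73 points detectable with 80% power. If losses are few and late, little is at stake.

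**A reader might infer that LOCF will favour the balloon technique, or that the result will be biased.** The documents do not support either. Section 4.3 foresees loss but not imbalance. The better functional recovery expected in section 2 fits a constant gain as well as a faster one, and the bias can run either way or cancel.

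**A reader might infer that equal dropout is enough protection.** It is not. Timing and remaining recovery must match too, and power still falls.

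**The PPS is already planned.** It would expose an LOCF artefact, but only if loss, non-compliance and protocol violations are all unrelated to outcome.

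**The mixed model is not always better.** This also stands. If loss depends on the unseen month 12 score, it was biased by about −0.2 to −0.45 points in two assumed cases, against −0.15 to −0.29 for LOCF (completers −0.43 to −0.85). When only month 12 is missed, LOCF has slightly more power: 78% against 77–78% (compound symmetry) or 74–77% (unstructured) on the steep course. In the worst case examined (flatter course, correlation 0.4) it is 80% against 77% and 74–75%.

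**The flow chart schedules HSS scores and has no Rasmussen row.** That conflict with the abstract and sections 5.3 and 6.1 is separate and is not evidence about LOCF. It matters here only because a model needs a named score; if HSS is what is collected, the point figures above do not apply.

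**Conclusion.** The concern holds as a conditional risk and should be fixed; confidence is medium. It is certain from the text that LOCF is the FAS's only missing-data rule. It follows by algebra that the rule biases the arm difference whenever share lost times recovery still to come differs between arms, and not otherwise when loss is unrelated to outcome. How large the bias will be, and in which direction, cannot be told from the documents.

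On the steep assumed course the effect runs from negligible (late loss, small imbalance) to about 1 point and 13% type I error (early random loss, 5% v 20%). The 13% should not be read as the error rate when exactly 1 v 4 patients are lost, which is about 8%. The power cost of early loss does not depend on any imbalance.

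**What to change.** First reconcile the Appendix I flow chart (HSS) with the abstract and sections 5.3 and 6.1 (Rasmussen), and state which knee score is collected at each visit. Then replace the LOCF sentence in section 8.1 with text such as:

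> The [named knee score] is analysed in the FAS with a repeated-measures mixed model containing arm, visit and arm by visit, using all observed visits without imputation. Estimation is by REML with Satterthwaite degrees of freedom, a [pre-stated covariance structure] and a [pre-stated fallback] if it does not converge. The primary contrast is the arm difference at [visit pre-stated by the sponsor]. LOCF is a sensitivity analysis. The number of patients with no postoperative score is reported by arm.

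The last sentence is needed because the first scheduled Rasmussen visit is month 1; a patient lost before then has nothing to carry forward. With 40 patients the sponsor should weigh a structured covariance (more power if correct) against an unstructured one (fewer assumptions).

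The cost is a few lines of text and slightly more analysis work, with no new visits. The model relies on a missing-at-random assumption and carries the two drawbacks shown above: it can be more biased than LOCF if loss depends on the unseen final score, and it has slightly less power when only the last visit is missed.

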8.2 Statistical analysis plan

There was no significant difference in age, gender, fracture type and other aspects between the two groups ($P>0.05$). Through epidemiological or statistical expert guidance, the experimental group and the control group data were analyzed using SPSS 22 statistical software, the measurement data in SX, using t test, count data expressed as a percentage, using X - test, $P < 0.05$, the difference has statistical significance, and draw the relevant charts with RevMan software.

9. Data management and statistical analysis

9.1 Filling and transferring of case report form

The case report form (CRF) was filled out by the researchers. The data in CRF were derived from original records and physical and chemical examination reports and other original documents and should be consistent with the original documents. Any observation and examination result in the test should be completed in time, correctly, completely, clearly, standard and truly in CRF, and should not be changed at will. All the items in the CRF are required to fill in, not empty or missed. If necessary, CRF data correction, fill in the data modification

9.2 Data input and modification

Data entry and management by the responsible investigators. Using EDC data entry system to establish a dedicated database for data entry and management, in order to ensure the accuracy of data, by two data managers independently double input and proofreading. The data entry process any data modification system are recorded.

The existence of the case report form questions, the data administrator will produce FAQ table (DRQ), and the issue of asking researchers by CRA, researchers should answer as soon as possible and return data, modify, and confirm the administrator for data entry on the answer, when necessary, can be re issued DRQ.

